### 3.3.1.4 **Determination of Subjects for Analysis**

Only those subjects that have completed both a baseline and 6-month 48 hour Holter monitor or are 6-month effectiveness failures based on other criteria will be included in the main analysis cohort for this objective.

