Cardioversion Log: At protocol defined study visits and unscheduled study visits the cardioversion log will be updated with the date of any electrical cardioversions that have been performed since last clinic visit.

48-hour ambulatory ECG monitor: Will be collected at protocol defined study visits to determine heart rhythm. Examples of ambulatory ECG monitors are Holter monitors, wearable wireless adhesive ECG monitors (e.g. ECG patch monitors).

For the Baseline ambulatory ECG monitoring, this should be completed within the 3 months prior to the index ablation procedure to document study subject has continuous AF. Subjects may be asked to repeat an ambulatory ECG monitoring session if less than 24 hours of analyzable monitoring time is obtained or continuous AF is not demonstrated. The ambulatory ECG monitoring technology used at the 6-month visit should be the same as the technology used at the baseline visit.

Trans-thoracic echocardiogram (TTE): Will be collected at Baseline or within previous 6 months of the index or reablation procedure to determine atrial volume and size.

Trans-esophageal echocardiogram (TEE): Will be collected within 48 hours prior to the index or reablation procedure to rule-out left atrial thrombus.

If a left atrial thrombus is visualized during pre-procedure TEE, the study subject will not undergo the study ablation procedure at that time.

MRI/CT scan (Chest): Will be done prior to ablation procedure and 3 months post index ablation procedure for the assessment of PVS in subjects in the PVS assessment cohort.

For the Baseline scan, this should be completed within the 3 months prior to the index ablation procedure.

The imaging technology (MRI, CT) used at Baseline pre-procedure scan must match the 3-Month post-procedure scan technology for a given study subject.

International normalized ratio (INR): Blood will be drawn at each study visit (i.e. within the study visit window) to determine the subject's INR.

Two (2) INR levels demonstrating the study subject is therapeutic on VKA are required in the 30 days prior to the index ablation procedure. INR draws from other health care providers are permitted.

Esophagus visualization: Perform visualization prior to ablation procedure using site standard procedure.

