12.3.1.4 Analysis Methods

Acute effectiveness for each subject will be determined as described in section 12.3.2. In order for a subject to meet the acute procedural success criterion for the 6-month effectiveness endpoint, the subject must be an acute procedural success for their index and reablation procedure (if required). Ambulatory ECG monitor recordings will be completed at the baseline and 6-month post final Phased RF ablation visit. Ambulatory ECG recordings will be read and summarized by the Holter core laboratory. For the baseline and 6-month post-ablation procedure ambulatory ECG recording, the percentage of time in clinically significant AF (AF > 10 minutes) will be calculated as the total number of seconds in clinically significant AF divided by the total analyzable ambulatory ECG monitor recording time in seconds. The percent reduction from baseline will be calculated as the difference of the percentage of time in clinically significant AF between the baseline and 6-month post-ablation procedure visit divided by the percentage of clinically significant AF at baseline. Subjects with at least a 90% reduction in clinically significant AF will be considered successful for the ambulatory ECG component of 6-month effectiveness endpoint. Adjustments to all cardiovascular medications including antiarrhythmic drugs and dates of all DC Cardioversions will be captured on the case report forms.

Only those subjects that have a baseline and 6-month post-procedure 48-hour ambulatory ECG monitor data that are readable by the core lab or are missing ambulatory ECG data but were 6-month effectiveness failures based on other criteria at the time of the visit cutoff date will be included in the analysis of this

objective. Specifically, the denominator for the 6-month effectiveness rate will include all subjects that had at least one Phased RF ablation procedure where an investigational catheter was deployed into the left atrium and have baseline and 6-month ambulatory ECG monitor data available or do not have ambulatory ECG data available but were 6-month effectiveness failures based on other criteria. The numerator will include all subjects in the denominator that meet all four 6-month effectiveness conditions. A two-sided 95% exact confidence interval for 6-month effectiveness rate will be calculated.

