12.3.1.5 Determination of subjects for analysis

Only those subjects that have completed both a baseline and 6-month 48 hour ambulatory ECG monitor or are 6-month effectiveness failures based on other criteria will be included in the main analysis cohort for this objective.

In the event that the recording duration of the ambulatory ECG monitor exceeds 48 hours (e.g. a 7 day ECG patch monitor is used), the AF burden will be computed by the core laboratory for the initial 48 hours only.

Likewise, in the event the ambulatory ECG monitor is less than 48 hours (e.g. due to inadequate ECG patch monitor fixation, subject compliance) the AF burden will be determined by the core laboratory based on the total usable or analyzable recording period. Subjects may be asked to repeat an ambulatory ECG monitoring session if less than 24 hours of analyzable monitoring time is obtained. Subjects with less than 24 hours of usable ambulatory ECG recording time will be considered missing in the analysis (unless they are 6-month effectiveness failures based on other criteria) and included in sensitivity analyses as described below.

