### 3.3.1.3 Analysis Methods

Acute effectiveness for each subject will be determined as described in section 3.3.2.2. In order for a subject to meet the acute procedural success criterion for the 6-month effectiveness endpoint, the subject must be an acute procedural success for their index and reablation procedure (if required). Holter recordings will be completed at the baseline and 6-month post final Phased RF ablation procedure. Holter recordings will be read and summarized by the Holter core laboratory. For the baseline and 6-month post-ablation procedure Holter recording, the percentage of time in clinically significant AF (AF > 10 minutes) will be calculated as the total number of seconds in clinically significant AF divided by the total Holter recording time in seconds. The percent reduction from baseline will be calculated as the difference of the percentage of time in clinically significant AF between the baseline and 6-month post-ablation procedure visit divided by the percentage of clinically significant AF at baseline. Subjects with at least a 90% reduction in clinically significant AF will be considered successful for the Holter component of 6-month effectiveness endpoint. Adjustments to all cardiovascular medications including antiarrhythmic drugs and dates of all DC cardioversions will be captured on the case report forms.

Only those subjects that have a baseline and 6-month post-procedure 48-hour Holter data that are readable by the core lab or are missing Holter data but were 6-month effectiveness failures based on other criteria at the time of the visit cutoff date will be included in the analysis of this objective. Specifically, the denominator for the 6-month effectiveness rate will include all subjects that had at least one Phased RF ablation procedure where an investigational catheter was deployed into the left atrium (i.e. placed in the left atrium and phased RF energy delivered) and have baseline and 6-month Holter data available or do not have Holter data available but were 6-month effectiveness failures based on other criteria. The numerator will include all subjects in the denominator that meet all four 6-month effectiveness conditions. A two-sided 95% exact confidence interval for 6-month effectiveness rate will be calculated.

[REDACTED]

[REDACTED]

[REDACTED]

[REDACTED]

[REDACTED]

[REDACTED]

[REDACTED]

[REDACTED]

[REDACTED]

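### For 6-month effectiveness, the SAP's rules for deriving AF burden do not match the current protocol on short recordings, long recordings or the time denominator

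*SAP*

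**What the plan says.** **Protocol.** Section 7.7 allows more than one kind of monitor: "Examples of ambulatory ECG monitors are Holter monitors, wearable wireless adhesive ECG monitors (e.g. ECG patch monitors". Section 12.3.1.4 computes the percentage of time in clinically significant AF as AF seconds "divided by the total analyzable ambulatory ECG monitor recording time in seconds". Section 12.3.1.5 then covers recordings that are not 48 hours long:

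- Longer (its example is that "a 7 day ECG patch monitor is used"): "the AF burden will be computed by the core laboratory for the initial 48 hours only".
- Shorter: "the AF burden will be determined by the core laboratory based on the total usable or analyzable recording period".
- Too short: "Subjects with less than 24 hours of usable ambulatory ECG recording time will be considered missing in the analysis", unless the subject has already failed on another criterion. These subjects go to sensitivity analyses. Section 12.3.1.7 describes a tipping-point analysis.

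**SAP.** Section 3.3.1.3 requires "48-hour Holter data that are readable by the core lab", and 3.3.1.6 repeats the readability condition. Section 3.3.1.4 instead asks for completion: "Only those subjects that have completed both a baseline and 6-month 48 hour Holter monitor or are 6-month effectiveness failures" on other criteria. That sentence matches the opening of protocol 12.3.1.5, but the recording-length rules that follow it in the protocol are absent. The burden formula in SAP 3.3.1.3 divides by total Holter recording time, without limiting it to analyzable time. The visible SAP text does not mention patch monitors.

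The SAP's change history says that version 2 was aligned with version 5 of the clinical investigational plan.

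**The concern.** The ECG component is a threshold on a ratio: a reduction of at least 90% in the percentage of time in AF. Which hours count, and which recordings are long enough to count, can decide a subject's result. Protocol section 12 leaves data-handling rules to the SAP, and SAP section 1 says its analyses are those for the PMA and final reports. A programmer working from the SAP has no instruction for an 18-hour or a 168-hour recording, and has a denominator that differs from the protocol's.

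Short recordings can persist. Protocol 7.7, 7.13 and 12.3.1.5 say only that a subject may be asked to repeat a session with under 24 analyzable hours.

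At stake are the reported effectiveness rate and its confidence interval. Both documents say the main purpose of this endpoint is to show that operators were not so cautious about safety that treatment suffered. Crediting short AF-free recordings as successes would weaken that check.

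**Working it through.** **The plan's own precision figures.** Both documents assume 200 evaluable subjects and an exact two-sided 95% interval. Clopper-Pearson limits reproduce them:

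- 110/200 = 55%: 47.82% to 62.02%, width 14.20 points (stated: lower limit at least 47.8%, width at most 14.2%).
- 100/200 = 50%: 42.87% to 57.13%, width 14.27 points (stated: 42.9% and 14.3%).

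**Formula.** Reduction = (baseline % in AF − 6-month % in AF) / baseline %. Success needs at least 90%. Continuous AF at baseline is an inclusion criterion, so baseline burden is taken as 100% except where shown. Success then needs a 6-month burden of at most 10%, which is 4.8 h in 48 h.

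**Denominator.** The SAP column assumes that recording time means time worn.

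| Recording | Protocol (analyzable time) | SAP (total time) |
|---|---|---|
| 6 months: 48 h worn, 40 h analyzable, 4.4 h AF | 4.4/40 = 11.0%; reduction 89.0%; failure | 4.4/48 = 9.2%; reduction 90.8%; success |
| Baseline: 48 h worn, 40 h analyzable, all AF. 6 months: 48 h analyzable, 4.5 h AF | Baseline 40/40 = 100%; 6 months 4.5/48 = 9.4%; reduction 90.6%; success | Baseline 40/48 = 83.3%; 6 months 9.4%; reduction 88.75%; failure |

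The result can change in either direction.

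**Short recordings.** The SAP result depends on which of its own conditions is applied.

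| Recording | Protocol | SAP, if readable is the test | SAP, if completing 48 h is the test |
|---|---|---|---|
| 20 h, no AF | Missing; tipping-point analysis | ECG success | Excluded; not stated whether it counts as a missing Holter |
| 30 h usable | Included, burden over 30 h | Included | Excluded |

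Neither SAP reading reproduces the protocol.

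**Long recordings.** The SAP is silent. If the 48-hour cut were not applied to a 7-day (168 h) patch:

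- 6 h of AF, all in the first 48 h: 6/48 = 12.5% (failure) against 6/168 = 3.6% (success). With no later AF, this reversal covers more than 4.8 h and up to 16.8 h (10% of 168) of AF in the first 48 h.
- No AF in the first 48 h and 20 h later: 0% (success) against 20/168 = 11.9% (failure).

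**Effect on the rate.** The documents do not say how many recordings are affected, so k is an assumed range. The starting point is 110/200 = 55.0%.

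| k | k successes become missing | k successes become failures |
|---|---|---|
| 2 | 108/198 = 54.5% | 108/200 = 54.0% |
| 5 | 105/195 = 53.8% | 105/200 = 52.5% |
| 10 | 100/190 = 52.6% | 100/200 = 50.0% |
| 20 | 90/180 = 50.0% | 90/200 = 45.0% |

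If the SAP were instead read as requiring a completed 48 hours, the protocol rule would add 24 to 48 h recordings. Two added successes give 112/202 = 55.4%, and two added failures give 110/202 = 54.5%.

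**The case against.** The strongest reply is that the SAP specifies a 48-hour Holter throughout and that the core laboratory reads and summarises the recordings. The protocol gives the 48-hour cut to that laboratory. If the laboratory follows the protocol, the SAP formula receives 48-hour data and the 7-day examples do not arise. This stands. A reader might infer that the SAP scores a 7-day patch on 168 hours, but it contains no such instruction.

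A reader might also infer that the SAP admits any short recording as a success. That follows only from the readability condition. The completion condition in 3.3.1.4 would exclude an 8-hour recording, and also a 30-hour one that the protocol keeps. The SAP does not say which condition governs.

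Other points that stand:

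- Part of SAP 3.3.1.3 is redacted. SAP 3.3.2.3 shows that PROC FREQ statements are in that section, but a recording-length rule there cannot be excluded. Sections 3.3.1.4 and 3.3.1.6 show no redaction and no such rule.
- The protocol says the same monitoring technology should be used at baseline and 6 months, so the documents do not support a claim that the two recordings lose a common time base.
- The cause is probably version lag. The SAP still has 350 subjects and 40 centers, against 420 and 55 in the protocol. That explains the mismatch but does not remove it.
- The endpoint has no hypothesis, and study success rests on the stroke objective alone.

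None of this answers the denominator difference, which is a direct conflict in visible text.

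**Conclusion.** The point holds as a mismatch between the visible SAP text and the current protocol. There are three differences: no 24-hour minimum, no rule for recordings that depart from 48 hours, and total rather than analyzable time as the denominator. The denominator is the clearest conflict, although a reversal from it requires recording time to mean time worn. The short-recording difference depends on which SAP condition is applied. The long-recording difference matters only if the core laboratory's 48-hour cut is not applied.

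The size is unknown because the number of short, partly unanalyzable or long recordings is not given. Per two subjects in 200, it is about 0.5 point when successes become missing and 1 point when they become failures. The direction is not fixed. Only the reported effectiveness rate and its interval are affected. The primary stroke decision and its type I error are not. It should be corrected before the analysis, and it fits within a general update of the SAP to the current protocol.

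**What to change.** In SAP 3.3.1.3, 3.3.1.4 and 3.3.1.6:

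- State that a baseline or 6-month recording with under 24 analyzable hours is missing and enters the tipping-point analysis, unless the subject has failed on another criterion.
- State that burden comes from the first 48 hours of a longer recording and from the analyzable period of a shorter one.
- Change the denominator of the burden formula to total analyzable time.
- Replace Holter with ambulatory ECG monitor, so that patch recordings fall under the same rules.

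The cost is SAP wording and a few lines of derivation code. The evaluable set may change slightly. It shrinks if the SAP would otherwise have been applied on readability alone, and grows if it would have been applied as requiring a completed 48 hours.

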### 3.3.1.5 **Confidence Interval Width**

The 6-month effectiveness rate among all 138 subjects randomized to the ablation management arm in TTOP-AF was 55.8% (77/138; 95% CI: 47.1% - 64.2%). However, in this intention-to-treat analysis, 17 subjects missing their 6-month Holter assessment were included in the analysis as failures. If only subjects with 6-month Holter data available in TTOP-AF were included in the analysis (the analogous analysis cohort in this study) the 6-month effectiveness rate was 63.6% (77/121; 95% CI: 54.4% - 72.2%). However, the TTOP-AF protocol required amiodarone be discontinued 28 days prior to the 6-month visit, did not require discontinuation of other antiarrhythmic drugs or DC cardioversions until 5 days prior to the 6-month Holter assessment. Thus, while it is expected that the estimated 6-month effectiveness rate in this study will be greater than 50%, it may be less than 64% due to differences in allowed concomitant therapy use between studies.

Based on the following assumptions:

- Up to 350 subjects will be enrolled
- 300 subjects are required to complete the 30-day post-ablation visit and have the opportunity for a reablation procedure (i.e. complete 6-month visit) or complete the 30-day post-reablation visit if a reablation procedure is required
- Total of 40 study centers
- 9 months to activate the 40 centers
- Enrollment rate of 0.4 subjects per center per month once activated
- 30% of subjects will be re-ablated prior to their 6-month visit
- 10% annualized attrition rate

It was estimated via a simulation study that approximately 275 subjects would complete the 6-month Holter assessment. Assuming 200 subjects have evaluable baseline and 6-month Holter data and the observed 6-month effectiveness rate is 55%, then the exact 95% two-sided confidence interval should have a width no larger than 14.2% with a lower limit of at least 47.8%. Similarly, if the observed 6-month effectiveness rate is 50%, the confidence interval width should be no greater than 14.3% with a lower limit of at least 42.9%.

### **3.3.1.6 Missing Data**

Subjects will only be included in this analysis for the 6-month effectiveness objective if they have both a baseline and 6-month 48-hour Holter that are readable by the core lab or are missing a 48-hour Holter data and are 6-month effectiveness failures based on other criteria at the time of the visit cutoff date. However, should the issue of missing data arise, all ablated subjects that complete the 6-month visit at the time of the visit cutoff regardless of Holter data status will be included in a tipping point analysis to evaluate the impact of missing data. Specifically, subjects completing the 6-month study visit but missing the Holter assessment who are not 6-month effectiveness failures based on other criteria will be included as successes and then iteratively included as failures in the tipping point analysis.

### **3.3.1.7 Pre-specified Subgroup Analysis**

If more than one PVAC catheter model (PVAC or PVAC GOLD) is used during the VICTORY AF study a subgroup analysis will be performed to assess the 6-month post-procedural effectiveness by PVAC catheter subgroup as described in section 3.1.3.3.

## **3.3.2 Secondary Objective #2: Acute Procedural Success**

Confirm acute post-procedural effectiveness.

### **3.3.2.1 Hypothesis**

There is no pre-specified hypothesis associated with this secondary objective.

### **3.3.2.2 Definition Acute Procedural Success**

For the index Phased RF ablation procedure, acute procedural success is defined as meeting all four of the following conditions:

1. Only Phased RF catheters used in the left atrium to achieve procedure success  
AND
2. All accessible pulmonary veins were isolated (entrance block)
3. Complex fractionated atrial electrograms (CFAEs) and high frequency intracardiac electrogram amplitudes were mapped and ablated as necessary with Phased RF System
4. Sinus rhythm is restored at the end of the ablation procedure (with or without cardioversion)

For a reablation Phased RF procedure, acute procedural success is defined as meeting at least conditions (1) and (4) of the acute procedural success definition above.

### **3.3.2.3 Analysis Methods**

All ablation procedure parameters will be captured on the case report forms. For estimating the acute success rate, all subjects with an attempted ablation where at least one of the Phased RF catheters were deployed into the left atrium (i.e. placed in the left atrium and Phased RF energy delivered) will be included in the denominator. The numerator will include all subjects in the denominator who met all the conditions for acute procedural success defined above. A two-sided 95% exact confidence interval for the acute procedural success rate will be calculated. Subjects that have a reablation attempt will be considered acutely successful if they meet all the conditions for their index procedure and conditions 1 and 4 of the acute success definition for their reablation

attempt since the source of recurrent AF will be unknown. SAS code similar to the PROC FREQ statements in section 3.3.1.3 will be used to compute the two-sided 95% exact confidence interval for the acute success rate.

In addition to calculating the acute success rate on a per subject basis, the acute success rate will be calculated on a per procedure basis. The denominator for the per procedure rate will be all Phased RF procedures where at least one Phased RF catheter was deployed into the left atrium and Phased RF energy delivered. The numerator will be all Phased RF procedures in the denominator that meet the acute success definition. A two-sided 95% confidence interval for this rate will also be calculated using the method of Rao and Scott for clustered binary data since subjects may have up to two ablation procedures. A SAS macro to calculate the Rao and Scott confidence interval can be found in the directory:

V:\AF Solutions\VICTORYAF\Documents\Statistical\_Analysis\_Plan.

#### **3.3.2.4 Determination of Subjects for Analysis**

All ablation procedures that meet the cutoff date for the analysis of the primary objective where at least one Phased RF catheter was deployed into the left atrium will be included in the analysis.

#### **3.3.2.5 Missing Data**

There is not expected to be any missing data associated with the analysis of this objective since the objective is evaluated at the time of the procedure.

